Anyone in the study who tests positive for COVID-19 as part of the study (both Index Participants and Network Contacts) will be eligible for the CloseST study: a cohort study of individuals with COVID-19 infection. They will be offered additional test kits or clinic test referrals based on which study arm they were initially assigned. They will then be encouraged to get their close contacts tested as well. After the transition to Ellume test kits (planned for the start of December, 2021), we will no longer be able to monitor test results from self-testers. Self-testers who test positive must contact study staff to be enrolled in the study.

Figure 1: Overall study plan:

Study Sites:

This study will be conducted at three clinic sites across Philadelphia in the Public Health Management Corporation network.

PHMC Care Clinic – FQHC that focuses on serving people with HIV, viral hepatitis, and substance use disorders. Currently this study site provides COVID-19 testing mostly by appointment. Some walk-ins are allowed.

[name]
[name]

Congreso Health Center – FQHC that provides primary care to predominately Spanish-speaking population in North Philadelphia. Currently this study site provides outdoor COVID-19 testing by appointment only. Staff are expected to be fluent in Spanish and English.

[INACTIVE STUDY SITE]
[name]
[name]

Health Connection – FQHC

[name]
[name]

Rising Sun – FQHC

[name]
[name]

Mary Howard Health Center For The Homeless – FQHC that focuses on providing care to people who are experiencing homelessness. There is currently no study Interviewer carrying out recruitment activities at this clinic.
[INACTIVE STUDY SITE]

Table of Contents:

Manual of Procedures (MOP) is broken up into the following sections:

OVERVIEW OF STUDY

INDEX PARTICIPANTS

- a. Initial Recruitment
- b. Eligibility and verbal informed consent
- c. Baseline survey
- d. Testing and signed informed consent
- e. Randomization
- f. Intervention
- g. Study compensation
- h. Delivery of test results
- i. 8-week follow-up and study compensation

NETWORK CONTACTS

Self-test arm

- a. Informed consent and registration
- b. Home testing
- c. Delivery of test results

Test referral arm:

- a. Verbal informed consent and registration
- b. Signed informed consent
- c. Clinic test
- d. Delivery of test results

TEST RESULTS

MANAGEMENT OF POSITIVE COVID-19 TEST RESULTS

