Index Participants will receive five COVID-19 self-collection test kits at study enrollment to distribute to Network Contacts. Participants will be encouraged to distribute the test kits to individuals in their social network who are symptomatic, have a known exposure to COVID-19, or are otherwise perceived to be at high risk for COVID-19 due to potential exposures. Test kits will have a link to a study website which will guide test-takers through an online informed consent page and then onto a questionnaire. The participant will be provided a tutorial, list of drop-off sites and phone number to provide further assistance. Each individual will be offered follow-up care and counseling. Index participants will be asked to complete an online follow-up survey after 8 weeks.

Self-Collection Test Kits

The intervention will use COVID-19 self- collection PCR test kits that have been authorized under FDA Emergency Use Authorization. Test kits use a mid-nasal swab that is sent to a central lab, with results returning in 24 to 48 hours. Each kit includes a test swab, test tube, a prepaid return shipping envelope, and instruction sheet in English and Spanish.

December 2021 Update:

As of December 2021, the intervention will use Ellume rapid antigen tests (Ellume COVID-19 home test, Ellume Health, Brisbane, Australia) authorized under EUA. The antigen kits will use a Bluetooth-enabled test developer device, with test results only available through a smartphone app connected to the device. Test kit packages will include a study QR code linking the test kit to the index participant. If the network contact clicked the study QR code, test results were then reported to a secure web-based study portal.

Registration of test kits

Test kits must be registered online on the study website, and participants must consent to participate in the study to activate the test kits. Participants must provide a name, date of birth, and phone number to register test kits. If participants do not have access to the Internet, they may call study hotline and study personnel will obtain informed consent and register the individual online.

Control

Secondary distribution of COVID-19 test referrals

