For network contacts:

If Network Contacts test positive and enroll in the CloseST study, their REDCap ID number will become their “Referral ID number.” Their ID numbers will start with 1 and go up after that.

Study intervention:

Self-test kit arm procedures:

If randomized the self-test kit arm, the interviewer will go through script C “Index Participant randomized to self-test kit.”

The interviewer will retrieve a package of 5 self-test kits. Self-test kits will be kept in secure locations determined by the staff of the participating clinic sites.

Assigning test kits to the index participant:

- The interviewer will affix a sticker to each of the 5 test kits instructing them to download the Ellume app. It will also include a QR code for network contacts to scan with a smartphone and a URL that network contacts can type into a web browser on a smartphone. The QR code or link will send the network contact to a page on the Ellume app for them to have their test sample analyzed. All 5 test kits will have the same

QR code and URL. For the purposes of this study, the PIs have bought the domain name *testphilly.com*. Each URL that will accompany a QR code on a test kit will include a number. The numbers will start with 1, and go up sequentially (for example, *testphilly.com/1*, *testphilly.com/2*, *testphilly.com/3*, etc.). All 5 test kits given to the same index participant will have the same QR code and URL on them.

- Each test kit will have instructions on downloading the app, taking a sample using the test kit, and having the sample analyzed, attached to it with a rubber band.

Post-randomization assessment

The Interviewer will also ask the Index Participant the “Intentions” instrument.

Self-testing kits:

The Interviewer will provide an explanation to the index participant of how to distribute test kits to contacts and how to use test kits.

In order to use the test kits, a network contact will need to have a smartphone with Bluetooth capability, and they will have to download the Ellume app. and then go to the URL on the test kit or scan the QR code.

Index participants can give the test kit to anyone aged 2 or older.

Intervention instructions:

Participants will be encouraged to distribute the self-tests to individuals in their social network, including family members, with encouragement to deliver to network contacts ages 2 and older who:

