- 1) Has had a known exposure to COVID-19. If exposed, testing should ideally be done 5-7 days after the exposure.
- 2) Is symptomatic (fever, difficulty breathing, new cough, unusual fatigue, loss of taste or smell, rash on fingers or toes)
- 3) Is believed to be at high risk of COVID-19 due to multiple in-person interactions with others.

Update November 11, 2022:

In order to comply with changes in the FDA emergency use authorization of rapid antigen tests for SARS-CoV-2, individuals should be advised on appropriate use of test kits. This update supercedes the prior update in EUA in March 2022.

Participants who receive intervention with test kits:

- If individuals obtain an initial negative test result, they should:
 - o Test again 48 to 72 hours (2-3 days) if they have symptoms on the first day of testing
 - o Test 2 more times at least 48 hours apart if they do not have symptoms (A total of 3 times over 5 days)
- If individuals obtain an initial positive test result, no repeat testing is needed to confirm the result.

Note:

- If individuals test negative and need another test kit, **they can bring the study-issued test kit to a clinic to receive two additional Ellume test kits at no cost.**
- Only individuals who have proof of a **negative study-issued test can obtain two additional Ellume test kits** (to be picked up by at a study site). They must show proof of:
 - o 1) a test kit from the study
 - o 2) a negative result in the past 48 hours

Test referral Arm procedures:

For index participants randomized the self-referral arm, the Interviewer will go through script D **“Index Participant randomized to test referrals.”**

The index participant will receive 5 test referral cards with guidance on distributing them. They will also receive a text message with simple instructions to send to contacts on how to get tested, which they can then copy and send to contacts (See Script N.1. **“Referral for Index Participant in Test Referral arm.”**

Each card will be labeled with the **Index Referral ID number**. The Interviewer will then enter the 5-digit index referral number into that patient's record. Test referral cards will be kept in secure location at clinic sites.

Test referral cards:

- Test referral cards will have clinic information on where to get testing and instructions to return the card to the Interviewer in each of the clinic sites. If the Interviewer is unavailable at the time, the subject can also return the card to the front desk staff.

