2. If they have not signed an electronic consent form, interviewers will complete the informed consent form either electronically or the paper form.

Study Compensation

- There is no compensation for network contacts.

DELIVERY OF TEST RESULTS (for tester index participants and test-referral network contacts)

Research interviewers will be responsible for reviewing all self-test results and clinic test results on a daily basis.
Review of self-test results

Self-test results:

1. Positive test results will trigger a phone call (see Script I “Communication of test results – COVID-19 positive” for COVID-19 positive individuals).
2. Negative test results will trigger a phone call (see Script H “Communication of test results – COVID-19 negative”)

Review of clinic test results:

The interviewer will be responsible for reviewing all test results daily.

1. Negative test results: No call needed (clinic staff call participants)
2. Positive test results – Follow the script as indicated below for COVID-19 positive individuals.

MANAGEMENT OF POSITIVE COVID-19 TEST RESULTS

Summary:

All individuals who test positive for COVID-19 during the trial require contact for follow-up. Here, we lay out procedures depending on *who* is testing positive.

COVID-19 participants are divided into two groups: ST participants (those in the Self-Testing arm) and TR participants (those in the Test Referral arm) (See Figure 3).

Counseling on COVID-19

COVID-19 participants Protocol (See Script I “Communication of test results – COVID-19 positive”)

- If someone else picks up, ask for best way to get ahold of contact or best time to call back.
- Make at least one attempt within 24 hours of test result receipt.
- Each attempt = 2 back-to-back calls with a voicemail left.
- If no voicemail is available, try **at least 2 additional times within 48 hours** of test result receipt to reach them.
- Interviewers should make a **total of 4 attempts within 7 days** after the result of the test.
- If the individual is unable to be reached, you may mark “Unable to reach” as the final disposition.
- NEVER reveal test results to anyone else without first confirming identity.

Eligibility:

1. At least 18 years or older
2. COVID-19 positive test obtained in the study in the **past 14 days**
3. Has a working telephone number

Verbal Consent to join COVID-19 cohort

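### The 48-hour proof limit for free repeat kits runs out just as the symptomatic retest falls due

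*Combined protocol and SAP*

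**What the plan says.** The rule is in the combined protocol and SAP, under Intervention instructions for index participants, in the Update of November 11, 2022 and its Note. The update was written to follow a change in the emergency use authorization for rapid antigen tests.

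- **With symptoms, first result negative:** "Test again 48 to 72 hours (2-3 days) if they have symptoms on the first day of testing".
- **Without symptoms, first result negative:** two further tests separated by at least 48 hours, making three tests over five days.
- **Repeat kits:** contacts who test negative and need another kit are told that "they can bring the study-issued test kit to a clinic to receive two additional Ellume test kits at no cost".
- **Conditions:** the offer is limited to people who show two proofs. One is a kit issued by the study. The other is "a negative result in the past 48 hours".

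The update gives no grace period, no alternative proof and no instruction to collect the kits before the retest is due. The study scripts, the instructions attached to each kit and the SOPs are named in the document but not reproduced in it.

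**The concern.** A contact may well look for a second kit only when the second test is due. For a symptomatic contact that is 48 hours or more after the negative, and by then the proof has expired. People with symptoms are also one of the three groups to whom index participants are asked to give kits, so this is not a fringe group.

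What is at stake is access to the recommended retest. A symptomatic contact whose first test was falsely negative, and who comes to the clinic inside the recommended window, leaves without the free kit that the update offers.

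The effect on trial data is small at most, and the document does not allow it to be sized:

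- **Primary outcome.** It counts index participants linked to at least two contacts who completed testing. A contact covered by the Note has already tested, so a retest does not change it.
- **Results reaching the study.** The December 2021 Update under Self-Collection Test Kits says "If the network contact clicked the study QR code, test results were then reported to a secure web-based study portal". The Overview of study says "we will no longer be able to monitor test results from self-testers". The QR sticker is described only for the index participant's five kits ("All 5 test kits given to the same index participant will have the same QR code and URL on them"), not for replacement kits. A positive retest may therefore never be recorded.
- **CloseST.** Entry requires "At least 18 years or older", and a self-test contact must make the call personally.
- **Positivity rate.** The Outcomes section does not say whether this secondary outcome is per test or per contact, so even the direction of any effect is unclear.

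**Working it through.** The plan states no figure to reproduce here. The check compares two time intervals, with *t* the number of hours since the first negative result.

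**Inputs, all from the Update of November 11, 2022 and its Note**

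- Entitlement to repeat kits: 0 ≤ *t* ≤ 48
- Symptomatic retest window: 48 ≤ *t* ≤ 72, length 72 − 48 = 24 h
- Schedule without symptoms: three tests at least 48 h apart, within five days

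**Symptomatic contacts, current rule**

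Overlap = min(48, 72) − max(0, 48) = 48 − 48 = 0 h of 24 h. The intervals share only the point *t* = 48.

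| First visit (*t*) | Kits given? | Inside retest window? |
|---|---|---|
| 24 h | yes | no, too early |
| 47 h | yes | no, too early |
| 48 h | yes | yes, at the boundary |
| 49 h | refused | yes |
| 60 h | refused | yes |
| 72 h | refused | yes |

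Example: after a negative at 09:00 on day 1, entitlement ends at 09:00 on day 3. The retest window runs from that moment to 09:00 on day 4.

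**Symptomatic contacts, 72-hour limit**

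Overlap = min(72, 72) − max(0, 48) = 72 − 48 = 24 h of 24 h.

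**Contacts without symptoms**

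Let *D* be the length of the five days in hours. A second test that still leaves 48 h before the third must be done by *D* − 48. The useful time added by a 72-hour limit is min(72, *D* − 48) − 48. The document does not define *D*, so three readings are shown:

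| Reading of five days | *D* | Latest second test | Added by 72 h limit |
|---|---|---|---|
| Four intervals of 24 h | 96 h | 96 − 48 = 48 h | 48 − 48 = 0 h |
| Calendar days, first test 09:00 on day 1 | 120 − 9 = 111 h | 111 − 48 = 63 h | 63 − 48 = 15 h |
| Five full days | 120 h | 120 − 48 = 72 h | 72 − 48 = 24 h |

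These are hours, not shares of contacts. With no arrival times in the document, they cannot be turned into a number of people refused or positives missed.

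**The case against.** The strongest reply is that the rule works as a collection deadline. It closes when the first retest falls due, so a contact who meets it has the kits at home in time. Two kits are enough for either schedule. That is a coherent design, and it stands: the plan does not contradict itself.

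Four further points have some force.

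- **Unseen instructions.** Advice to collect early may already be in the scripts, kit instructions or SOPs. If so, half of the proposed change is already in place. Such advice would still not help someone who arrives at 49 hours or later.
- **Other sources of a kit.** A contact may get an unused kit from the index participant's five, and nothing restricts the retest to a study kit. This narrows the group affected but does not remove it.
- **Counting in days.** The update also expresses the window as two to three days. If sites count in days, a contact arriving on day 2 is both eligible and due. Day 3 remains uncovered.
- **Any limit refuses someone.** Under a 72-hour limit, a contact arriving close to 72 hours has little time left to test, and for contacts without symptoms the gain may be nil. This is a fair limit on the benefit. It does not justify a cut-off at the start of the symptomatic window, for which the document gives no reason.

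The group is narrow: self-test contacts testing after November 11, 2022, with a first negative, no spare kit and a first visit after 48 hours. That bears on how much the point matters, not on whether a late arrival is refused.

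**Conclusion.** The concern holds. As written, the offer of free repeat kits covers 0 of the 24 hours in which the same update asks symptomatic contacts to retest, apart from the 48-hour boundary itself. This rests on reading both limits in hours and on sites applying the proof requirement as stated. Counting in days softens the boundary but leaves day 3 uncovered.

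The point is minor. It concerns access to a recommended retest, with a small safety gain for symptomatic people. No effect on the primary outcome is claimed, and any effect on secondary or CloseST outcomes is probably small and of unclear direction. The change is worth considering because it costs so little.

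**What to change.** In the Note to the Update of November 11, 2022, change the second proof item so that a negative result from the past 72 hours is accepted. Add one line asking contacts to collect the two kits within 48 hours of the first negative where they can, so that the kits are in hand when the retest is due. The added line also eases the problem of arrivals close to 72 hours.

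The cost is one number and one line in the Note and the matching site instruction, plus two kits for each contact who comes between 48 and 72 hours. Both proofs stay in place, and the number of kits per person does not change. Randomization, outcomes and analysis are untouched.

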C-STRAND – COVID Self-Testing through Rapid Network Distribution

This Protocol is created by the Clinical Trial investigators and the Clinical Research Computing Unit for C-STRAND. The purpose of this document is to detail procedures necessary to complete the Case Report Forms and provide an overview of the data flow. This manual is intended to convey instructions for the collection of data so that it may be entered into the data management system.

C-STRAND ClinicalTrials.gov NCT04797858
CloseST ClinicalTrials.gov NCT04847479

Created by:
[name]
Clinical Trial Director
Division of Infectious Diseases
Perelman School of Medicine
University of Pennsylvania, PA
[contact]

[name] MSCE
Principal Investigator
Division of Infectious Diseases
Perelman School of Medicine
University of Pennsylvania, PA

Updated: November 28, 2022

[figure not shown]
Overview of study:

Widespread testing and contact tracing are critical to controlling the COVID-19 epidemic. One promising approach to increase test uptake is the secondary distribution of self-tests, where an individual distributes test kits to contacts in their social network and encourages them to self-test. We will conduct a 1:1 randomized controlled trial randomizing individuals to receive either *multiple* self-test kits to distribute within their social circles, or referrals for standard clinic-based tests.

We will recruit individuals seeking COVID-19 testing or presenting to PHMC clinic sites for other types of appointments and randomize them to receive either *multiple* (1) home test kits or (2) clinic test referrals to encourage people in their social networks to get tested. Individuals who distribute test kits or test referrals will be designated “Index Participants,” or Category 1 participants. Individuals who receive test kits or test referrals from Index Participants are called “Network Contacts.” Network Contacts are divided into two categories based on what test distribution method they received: Category 2 if they received home test kits, and Category 3 if they received clinic test referrals. Our primary outcome of interest is to see which strategy (home test kits or clinic test referrals) got more Network Contacts to obtain testing within 8 weeks of the Index Participant getting tested.

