APPENDIX DOCUMENT: STUDY SCRIPTS

APPENDICES: SOPs

[SOP: Rising Sun](#)

[SOP: Health Connection](#)

[SOP: EPIC EHR](#)

[SOP: Ellume test kit labels](#)

[SOP: Index Participant recruitment](#)

[SOP: Required baseline survey questions](#)

[SOP: Tracking referral IDs](#)

[SOP: Participant Payments](#)

[SOP: Follow-up surveys](#)

[SOP: Network Contacts](#)

[SOP: Recruitment Tracker](#)

OVERVIEW OF STUDY

Trial Design

The C-STRAND study is a 1:1 randomized control trial randomizing participants to receive either multiple self-collection test kits or multiple referrals for clinic-based tests to distribute within their social networks. These individuals, called *Index Participants*, will be encouraged to distribute self-collection test kits or test referral cards to others in their social networks, called *Network Contacts*. Network Contacts can include household members, friends, family, colleagues, or others in Index Participants' social networks. We will evaluate COVID-19 test uptake among Network Contacts.

To achieve our second aim, the CloseST study is a cohort study of both index participants and network contacts diagnosed with COVID-19 from the C-STRAND trial. Participants will then receive additional self-collection test kits or referrals for clinic-based tests to distribute to close contacts, based on their treatment assignment group from the C-STRAND trial. We will compare test uptake among close contacts of individuals with COVID-19.

Allocation

In the C-STRAND trial, we will use permuted block randomization with varying block sizes stratified by study site to assign Index Participants to receive multiple self-collection test kits or multiple referral cards for standard clinic-based tests. Investigators will have access to arm assignment on a need-to-know basis only, but participants and research assistants will not be masked with respect to study arm.

For the CloseST study, Index Participants and Network Contacts who test positive will be assigned to the intervention arm (receiving multiple self-collection test kits) or control arm (test referrals) according to their original assigned arm in the C-STRAND trial.

Intervention

Secondary distribution of COVID-19 self-collection test kits

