- The interviewer will ask individuals about close contacts
- The interviewer will elicit close contact information, and help the individual prioritize who to give testing to.
- The interviewer will instruct COVID-19 participant to tell close contacts to quarantine, monitor symptoms, and that if desired, they can obtain testing at PHMC clinics
- The interviewer will then send the COVID-19 participant a “COVID-19 referral text” (See Script N.3 “[Text message for COVID-19 positive contact test referral](#)”) that they can forward to contacts.

Network contacts in self-test kit arm who test positive:

- Need to be registered in RedCap

Study compensation:

Index Participants:

- At the end of the phone call, the interviewer will ask the COVID+ participant if they still have their ClinCard.
 - If they have their ClinCard, this will be reloaded with \$15.
 - If they do not have their ClinCard, they can be sent a \$15 compensation through an electronic gift card (Target gift card or electronic ClinCard, if available).

Network Contacts

- Study compensation for network contacts who enroll in COVID+ cohort:
 - They will be able to receive **\$30** as target virtual gift cards as a single one-time payment.

Sample Size

The sample size for the C-STRAND trial was calculated based on the primary outcome of Aim 1. Power calculations were completed using STATA 15.1 (STATA Corp, College Station, TX). With an estimate that 45% in the control group achieve success, defined as at least two network contacts completing testing, we calculated a sample size of 1048 needed to detect a 10% difference (two-tailed alpha of 0.05, power of 90%). If in fact we observe a success rate as low as 25% in the control group, with a sample size of 1048, we will have 90% power to detect as small as an 8% difference.

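### At a 25% control rate, 1048 participants give about 82% power for an 8-point increase, not 90%; 90% power needs about 9.1 points

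*Combined protocol and SAP*

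**What the plan says.** The Sample Size section makes two statements about the primary outcome, the proportion of Index Participants with at least two Network Contacts tested.

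- **Main calculation.** "With an estimate that 45% in the control group achieve success", and on that basis "we calculated a sample size of 1048 needed to detect a 10% difference", with two-tailed alpha 0.05 and 90% power.
- **Low-uptake scenario.** If "we observe a success rate as low as 25% in the control group", then "with a sample size of 1048, we will have 90% power to detect as small as an 8% difference".

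Neither statement gives the direction of the difference. The Trial Design section fixes equal allocation ("The C-STRAND study is a 1:1 randomized control trial"), so 1048 means 524 per arm. The overview gives the direction the trial hopes for: "One promising approach to increase test uptake is the secondary distribution of self-tests".

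**The concern.** The second statement is the plan's only account of its power if control uptake is well below the planning value. It looked doubtful because moving the control rate from 45% to 25% shrinks the binomial variance only modestly when the intervention rate lies above control. That does not look enough to bring the detectable difference from 10 points down to 8 at the same N and power.

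If the figure is wrong, readers of the plan, and later readers of a non-significant result with low control uptake, would credit the trial with more sensitivity to an 8-point benefit than it has.

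**Working it through.** **Inputs**

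- Two-sided alpha 0.05 (z = 1.960) and power 90% (z = 1.2816): Sample Size.
- N = 1048; control rates 45% and 25%; differences of 10 and 8 points: Sample Size.
- 1:1 allocation, hence n = 524 per arm: Trial Design.
- Direction: an increase over control. This is inferred from the overview and tested in step 5.
- No dropout allowance. The section gives none and none is applied.

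**Formulas** (two-proportion z-test, p̄ = (p1 + p2)/2)

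- n per arm = [1.960·√(2p̄(1−p̄)) + 1.2816·√(p1(1−p1) + p2(1−p2))]² / (p1 − p2)²
- Power = Φ{ [ |p1 − p2| − 1.960·√(2p̄(1−p̄)/n) ] / √([p1(1−p1) + p2(1−p2)]/n) }

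**Step 1. Reproduce the headline N (45% vs 55%).** p̄ = 0.50, 2p̄(1−p̄) = 0.500, sum of variances = 0.495.

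n = (1.3859 + 0.9017)² / 0.01 = 523.3, so 524 per arm and **1048** in total. Power at 524 per arm is 90.04%. The plan's figure is matched exactly, so this is a suitable formula for the next sentence.

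**Step 2. Power for 25% vs 33% at the same N.** p̄ = 0.29, 2p̄(1−p̄) = 0.4118, sum of variances = 0.1875 + 0.2211 = 0.4086.

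- Null SE = √(0.4118/524) = 0.02803; times 1.960 = 0.05494.
- Alternative SE = √(0.4086/524) = 0.02792.
- Power = Φ[(0.08 − 0.05494)/0.02792] = Φ(0.897) = **81.5%**.

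**Step 3. N needed for 25% vs 33% with 90% power.** n = (1.2577 + 0.8192)² / 0.0064 = 674.01, so 675 per arm and **1350** in total, which is 302 more than planned.

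**Step 4. Detectable increase from 25% with 524 per arm.** Solving the power formula for the difference gives **9.12 points** at 90% power (25% to about 34.1%) and 7.84 points at 80%.

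**Step 5. Could another reading give 90%?**

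| Reading | Result |
|---|---|
| Increase, unpooled variance | 81.7% |
| Increase, arcsine | 81.6% |
| Increase, continuity-corrected | 79.6% |
| Increase, simulated site-stratified CMH test (3 equal sites assumed) | 81.7% (79.9% with continuity correction) |
| 8 points as a rounded 8.49 | 85.7% |
| One-sided alpha 0.05 | 88.8%, but the plan is two-tailed |
| 1048 per arm | 98.1%, but contradicts the headline N |
| 8% as a relative change (25% to 27%) | about 11% |
| Decrease, 25% to 17% | 89.0%; detectable decrease at 90% is 8.13 points |

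The decrease comes closest. Applied to the main calculation, however, a decrease (45% to 35%) gives 502.3, so 503 per arm and 1006 in total, or 1046 with continuity correction. Only the increase gives 1048 exactly.

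**The case against.** The strongest defence is that the plan says only that there is a difference, under a two-tailed test, and names no direction. For a decrease from 25%, the difference detectable with 90% power is 8.13 points, which rounds to the plan's 8. The continuity-corrected figure for 45% vs 35% (1046) also misses the headline by only two participants, so the headline does not exclude the downward reading as firmly as the uncorrected 1006 suggests.

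This shows that any correction must name the direction, and it may explain how the figure arose. It does not make the sentence right for its purpose. The trial asks whether kits raise uptake, the exact match for 1048 is upward, and a two-tailed test still has 81.5% power against 25% to 33%.

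The second objection concerns weight, and much of it stands:

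- The sample size rests on the 45% vs 55% calculation, which is correct.
- No enrolment target, analysis or decision rule uses the 8-point figure.
- For the trial's own 10-point target, power at a 25% control rate (25% vs 35%) is 94.3%, higher than at 45%.
- Power of 82% is still above 80%, a level the plan itself uses in one CloseST calculation.
- What a null result excludes depends on its confidence interval, not on a planning statement.

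These points limit the consequences; they do not alter the figure.

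**Conclusion.** The low-uptake sentence is wrong as written for the effect the trial is designed to find. At 25% control success with 1048 participants, power for an 8-point increase is about 82%. The type II error is therefore 100 − 81.5 = 18.5%, against the 10% stated. The detectable increase at 90% power is understated by about 1.1 points (9.12 − 8).

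This rests on the plan's own alpha, N and allocation, on full outcome data, and on reading the difference as an increase. The choice of test statistic moves the power only between about 79.6% and 81.7%. The three-equal-sites simulation is an assumption, because the plan gives no split by site, but the result does not depend on it.

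**What to change.** Replace the sentence with wording such as: *If the control success rate is as low as 25%, 1048 participants give about 82% power to detect an 8-point increase (25% to 33%) and 90% power to detect an increase of about 9.1 points (25% to about 34.1%); power for a 10-point increase is about 94%.* State in the main calculation, too, that the 10-point difference is an increase from 45% to 55%.

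The cost is a text edit and a less favourable stated figure. Enrolment, randomization and the analysis stay as they are. The sponsor can confirm the numbers with the software already named in the section.
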